4.4.3 Prohibited Food

Consumption of grapefruit juice is associated with inhibition of CYP1A2 and should be avoided during treatment with pirfenidone.

No special diet or dietary restrictions are otherwise designated in the study, unless recommended by the investigator for the treatment of adverse events.

4.4.4 Additional Restrictions

Patients should stop smoking at entering the treatment period (not less than 28 days before the start of treatment) as smoking is known to induce metabolism of the study drug and thus attenuate treatment effect. Smoking patients will not be enrolled in the study.

All participants will be warned of the potential photosensitivity skin adverse reactions and will be advised to use sunscreens during exposure to direct sunlight.

4.5 STUDY ASSESSMENTS

Study procedures are defined as laboratory tests, spirometry, DL_{CO} measurement, ECG, HRCT scan, directed medical history, physical examination, vital signs, height, weight, GAP risk assessment, 6MWT and Borg Scale, EQ-5D questionnaire, procedures for eliciting AEs and any changes to existing treatment regimens.

Patients will be followed through the Follow-up visit scheduled 2-4 weeks after treatment completion on Week 26 (± 1) or until entry into the long-term follow-up (rollover study), whichever occurs earlier. Patients who undergo lung transplantation or who choose to withdraw from study procedures early will be followed for vital status until Week 26.

Please see [Appendix 1](#) for the schedule of activities to be performed during the study.

Pirfenidone—F. Hoffmann-La Roche Ltd

4.5.1 Informed Consent Forms and Screening Log

Written Informed Consent for participation in the study must be obtained before performing any study-related procedures. Informed Consent Forms for enrolled patients and for patients who are not subsequently enrolled will be maintained at the study site.

An additional Informed Consent visit may be performed prior to the start of the Screening procedures and an appropriate review of the patient's clinical data relevant to the IPF diagnosis is done (see [Appendix 1](#)).

All screening evaluations must be completed and reviewed to confirm that patients meet all eligibility criteria within 4 weeks before enrollment. The investigator will maintain a screening log to record details of all patients screened and to confirm eligibility or record reasons for screening failure, as applicable.

All patients should be notified of the necessity to use safe contraceptive methods during participation in the study and 28 days after its completion or discontinuation (see [Section 4.1.1](#)).

4.5.2 Medical History and Demographic Data

Medical history includes clinically significant diseases, surgeries, cancer history (including prior cancer therapies and procedures), reproductive status, smoking history, use of alcohol, and drugs of abuse. In addition, all medications (e.g., prescription drugs, over-the-counter drugs, vaccines, herbal or homeopathic remedies, nutritional supplements) used by the patient within 28 days prior to treatment period will be recorded.

Demographic data will include age, sex, and self-reported race and ethnicity.

4.5.3 Physical Examinations

A complete physical examination should be performed at *an IC visit*, the Screening (*Washout*) and should include an evaluation of the head, eyes, ears, nose, and throat, the cardiovascular, dermatological, musculoskeletal, respiratory, gastrointestinal, genitourinary, and neurological systems. Any abnormality identified at baseline should be recorded on the General Medical History and Baseline Conditions eCRF.

At subsequent visits (or as clinically indicated), limited, symptom-directed physical examinations should be performed. Changes from baseline abnormalities should be recorded in patient notes. New or worsened clinically significant abnormalities should be recorded as adverse events on the Adverse Event eCRF.

Pirfenidone—F. Hoffmann-La Roche Ltd

4.5.4 Weight and Height

Weight and height will be measured as outlined in [Appendix 1](#). Height will be assessed at the Screening only.

4.5.5 Vital Signs

Vital signs will be measured by the investigator at the Screening and subsequent visits and include measurements of respiratory rate (breaths/ minute), pulse rate (beats/ minute), and systolic and diastolic blood pressure (mmHg), and axillary temperature (°C).

Respiratory rate will be measured in patient's resting position by counting chest movements per minute. Blood pressure and pulse rate will be measured in the supine/ sitting position. All recordings should be made using the same blood pressure recording instrument. Pulse rate is defined as radial pulse counted for 30 seconds in the supine/ sitting position. Body temperature is defined as axillary temperature (°C).

4.5.6 HRCT and Surgical Lung Biopsy

4.5.6.1 High-Resolution Computed Tomography

HRCT scans should be obtained before the Screening period as part of the routine practice for a patient. It may be used to confirm eligibility. For eligibility confirmation acceptable HRCT scans should be dated not earlier than 2 years before the Screening.

Baseline HRCT scans will be performed only in those patients who have no acceptable scans within 2 months before the start of treatment period (Day 1) and had no IPF exacerbations within this period. Semiquantitative analysis of CT scans with HRCT fibrosis score calculation should be performed in each timepoint as outlined in the schedule of study assessments (see [Appendix 1](#)).

All HRCT images are to be read by the site's local radiologist reader at first. Additionally, for eligibility confirmation the HRCT scans will be reviewed by two central readers who are radiologists with expertise in IPF. If the first expert (central reader-1) agrees with the local opinion, the second expert (central reader-2) will not review scans. If the first expert disagrees with the local opinion, the second expert should review scans.

HRCT acquisition in the study will be performed using the same scanning protocol. Images in a particular site should be read by the same local specialist. Further semiquantitative assessments of CT scans for fibrosis scores will be performed by one central reader. Detailed HRCT acquisition protocol and fibrosis scoring system are described in [Appendix 2](#).

Pirfenidone—F. Hoffmann-La Roche Ltd

All HRCT digital scans should be stored on a dedicated disk or tape at each study center. The images will be transferred electronically to the central readers responsible for interpretation of the images.

Data regarding the HRCT interpretation will be entered electronically into the vendor's database and incorporated into the clinical database.

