4.5.13.2 Screening Period (Day -28 to Day -1)

Procedures conducted during Screening will be used to determine the eligibility of each patient for study enrollment before initiation of treatment and to establish patient baseline status. If patients fail Screening due to a condition that subsequently resolves (e.g., infection), they may be considered for rescreening; however, these patients must be discussed with the study *Medical Monitor* or designee before rescreening. *In case of rescreening, the patient must be reconsented.*

The Screening period is defined as the time between the date of the first Screening procedure and Day -1 and may last up to 28 days. Screening procedures may be conducted on different days within the Screening period, if convenient. The order of procedures is not strict; however, basic requirements to be followed are given in gaps below.

The following procedures will be performed during Screening:

- Demographic data
- Review and update medical history and concomitant medications
- EQ5D questionnaire (should be performed before any other non-PRO assessments)

Pirfenidone—F. Hoffmann-La Roche Ltd

- ECGs (obtained before bronchodilator administration or on a separate day) All ECGs are to be obtained prior to other procedures scheduled at that same time (e.g., vital sign measurements, blood draws) and should not be obtained within 3 hours after any meal.
- Physical examination, vital signs, weight, and height
- Clinical laboratory assessments, including hematology, serum chemistries, serologic tests, and pregnancy test for women of childbearing capacity (blood samples must be drawn in fasted state)
- HRCT scan for baseline assessment (for patients with HRCT scans performed more than 2 months before the treatment period or with scans not meeting the imaging acquisition criteria outlined in Appendix 2)
- Review transbronchial lung biopsy/ BAL;
- Spirometry (FVC) (before and after bronchodilator administration with a 15 min delay). Collection and recording of the retrospective FVC values obtained in clinical practice over the last year.
- 6MWT and Borg Scale
- DL_{CO} (obtained before or 30 min after bronchodilator administration)
- GAP assessment
- Eliciting AEs

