6.4.3 Exploratory Efficacy Endpoints

HRCT fibrosis score

The HRCT findings will be evaluated using HRCT scoring system. One ILD radiologist will make assessments of 4 main findings in three zones of each lung. The six zone scores will be averaged to determine the total score for each patient. Score will be recorded at the initial diagnosis and after six and 12 months in a similar manner for further comparison. The mean \pm SD of HRCT fibrosis score like continuous variable will be determined obligatory at baseline, 6 *months* and optional at 12 months.

The values of HRCT fibrosis score at baseline, at Week 26 (optional) and Week 52 (optional) will be summarized in table with standard descriptive statistics for continuous variables and 95% CI for the mean.

Additionally, the absolute change of HRCT fibrosis score from baseline at Week 26 (optional) and Week 52 (optional) will be summarized in table with standard descriptive statistics for continuous variables and 95% CI for the mean.

The paired t-test will be performed to evaluate the changes in the variable from the baseline to Week 26 (optional) and Week 52 (optional), respectively. The type I error rate will be set to 5%.

Lung opacity (ground-glass attenuation)

The sign 'lung opacity' will be qualified separately using methodology described above for other signs, and its change over time will be assessed outside the framework of a total summed index of fibrosis (HRCT fibrosis score). Lung opacity should be graded as reticular abnormality to calculate the score for each zone, i.e. the percentage (%) area of opacity in a zone should be multiplied by the score of 2.

The percentage area of opacity at Baseline, at Week 26 (optional) and Week 52 (optional) will be summarized in table with standard descriptive statistics for continuous variables and 95% CI for *the* mean.

Additionally, the absolute change of percentage area of opacity from Baseline at Week 26 (optional) and Week 52 (optional) will be summarized in table with standard descriptive statistics for continuous variables and 95% CI for *the* mean.

Exacerbations

Pirfenidone—F. Hoffmann-La Roche Ltd

An exacerbation will be defined as an AE with special criteria, *i.e. only in case the exacerbation has led to death of a patient* (see [Section 5.2.1](#)). Rate of exacerbation will be reported in three following tables:

- Exacerbation cases during treatment period (until Week 26).

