⁴ Complete physical examination is performed at the Screening only (head, eyes, ears, nose, and throat, and the cardiovascular, dermatological, musculoskeletal, respiratory, gastrointestinal, genitourinary, and neurological systems). At subsequent visits (or as clinically indicated), only limited, symptom-directed physical examinations should be performed.

⁵ Height is assessed at the Screening only.

⁶ ECG should be performed after patient's resting in a supine position for at least 10 min, prior to other procedures scheduled at that same time (e.g., vital sign measurements, blood draws), bronchodilator administration and within 3 hours after any meal)

⁷ To confirm IPF will be applicable to use previously performed HRCT, if it is performed not earlier than 24 months before the Screening. Review of the SLB samples obtained within 4 years before the Screening should be performed centrally for eligibility confirmation. Histopathological evaluation, if not available, is not repeated at the Screening.

⁸ Transbroncheal biopsy or BAL are not mandatory and will only be reviewed at the Screening, if available, to exclude other causes of PF.

⁹ HRCT should be performed at the Screening only for patients having no validated procedure within 2 months prior initiation of treatment.

¹⁰ At screening, spirometry measurements of FVC should be performed before and after administration of albuterol (or sa butamol) from a metered dose inhaler (4 separate doses of 100 mg). Tests should be repeated after a 15-min delay. During further visits, bronchodilator test is not necessary to perform. Collection and recording of the retrospective FVC values obtained in clinical practice over the last year will be performed only *at the screening visit*.

¹¹ Blood samples must be drawn in fasted state. *Serologic tests: rheumatoid factor, anticyclic citrullinated peptide and antinuclear antibody titer.*

¹² Pregnancy test must be performed before first dosing on Day 1 and must be negative. If the urine test is positive, serum pregnancy test must be performed.

¹³ Questionnaires should be self-administered before the patient or clinician receives any information on disease status, prior to the performance of non-PRO assessments, and prior to the administration of study treatment, with the exception for Borg scale administered in conjunction with the 6MWT.

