Besides diagnostic purposes, HRCT is utilized in the study for response assessment and follow-up. HRCT is performed at initiation of the participation in the study and at the end of treatment. Adherence to the same technical parameters of acquisition, including posture, inspiration volume, imaging field, tube current and collimation, reconstruction interval, is the main requirement for repeated scanning in the course of the study. HRCT readings must not be assessed against X-ray scans. If the patient does not have X-ray scan at disease onset or at certain relevant timepoints the subsequent assessments should be performed with HRCT. HRCT frequency in the study is not strictly regulated.

Appendix 2

HRCT Protocol (cont.)

Table 1-1. Spiral scanning.

Parameter	< 16 slices per gantry rotation	≥ 16 slices per gantry rotation	< 16 slices per gantry rotation	≥ 16 slices per gantry rotation
Collimation (slice thickness)	1.25 mm	0.6-0.8 mm	1-1.5 mm	0.6-0.8 mm
Slice interval	1 mm	0.6-0.8 mm	10 mm	0.6-0.8 mm
Reconstruction algorithm	High resolution (bony)		High resolution, high spatial resolution algorithm, bony algorithm	
Spot reconstruction (field of vision, FOV)	Total lung volume		Total lung volume	
Level of inspiration	Unforced breath hold		End inspiration	
Physical parameters	120 kV/ automatical exposure		120 kVp / care dose	
Scanning time	As low as practicable for the scan (< 0.75 sec)		< 0.75 sec	
Window (level/ width)	-500...-700/1500 HU (Hounsfield unit) lung window		Pleural (lung) window	
Possible windows (level/ width)	-850/900 HU emphysema and cystic airspaces assessment +35...+45/400 HU mediastinal window		Lung window Soft window	
Recording/ archiving	CD/ DVD record in DICOM format and imagery viewer software Link to the cloud archive storage			

High-Resolution Computed Tomography Criteria for UIP Pattern

Morphologically IPF is based on the lung abnormalities typical for UIP. X-ray/ CT scans of patients with IPF are characterized by morphological abnormalities in lungs, i.e. UIP. The picture is characterized by various signs, typical or not typical for UIP (see [Table 1-](#)

Pirfenidone—F. Hoffmann-La Roche Ltd

Appendix 2

HRCT Protocol (cont.)

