Traction bronchiectases are uneven dilation of the bronchi and bronchioles as a result of the fibrotic shrinkage of the lung. Dilated bronchi may look like air strips with thin uneven (wavy) walls. Transversal dimension may show bronchi as cysts and bronchiole as microcysts in the peripheral parts of the lung. Location of the multiple air cysts around dilated bronchi may confound differentiation with the honeycombing symptom. Multidimensional reformations should be used for proper understanding of the morphological substrate.

Reticular abnormality

Reticular abnormality is a net of relatively thin lines, round- or polygon-shaped, on unchanged lung tissue or moderate lung opacity. Anatomically these lines represent abnormal interstitial lung elements resulting from intralobular interstitial tissue (less than 2 cm in size) thickening in UIP. These structures are usually presented with the fragments of acini septa. Septal lines (acini septa of a larger size), 1-2 cm in diameter, can also be involved in reticular abnormalities; however, they are usually less affected than smaller reticular elements.

Lung opacity (or ground-glass attenuation)

Lung opacity (or ground-glass attenuation) is a HRCT scialogical phenomenon characterized with mid-enhanced density of lung tissue, with lumina and walls of the bronchi, lung vessels, as well as foci and reticular abnormalities, if present. Morphological substrate of the lung opacity symptom is formed by the changes in the lung tissue with unaffected airness which are not captured by the CT acquisition. These changes may include thickening of the alveolar septa of any etiology, partial alveolar filling with different contents, alveolar shrinkage due to hypoventilation, enhanced lung perfusion and lung congestion. When honeycombing and traction bronchiectasis are not revealed, lung opacity may be one of the signs of active inflammation. When honeycombing and traction bronchiectasis are present, lung opacity is usually a sign of interstitial lung fibrosis.

Pirfenidone—F. Hoffmann-La Roche Ltd

Appendix 2

HRCT Protocol (cont.)

IPF exacerbations and complications

IPF exacerbation is characterized with appearance of new sites of lung opacity-like density and/ or sites of consolidation, or abrupt and fast exaggeration of the present alike abnormalities. Infiltration overlaps cortically on reticular abnormalities and honeycombing. In some cases honeycombing reduces partially or completely due to effusion in the cysts.

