Assessment of UIP signs

Assessment of UIP signs on HRCT will be performed using a semiquantitative method (see [Table 1-3](#)). Each lung will be divided vertically into three zones: upper zone, middle zone and lower zone. Margins between the zones on axial section are level of tracheal bifurcation and level of the right lower pulmonary vein. The upper lung zone is defined as the area of the lung above the level of the tracheal bifurcation, the lower lung zone is defined as the area of the lung below the level of the lower pulmonary vein and the middle lung zone is defined as the area of the lung between the upper and lower zones.

The HRCT findings will be graded on a scale of 1-4 based on the classification system: 1) normal attenuation; 2) reticular abnormality; 3) traction bronchiectasis; and 4) honeycombing. The presence of each of the above four HRCT findings should be assessed independently in three (upper, middle and lower) zones of each lung. The extent of each HRCT finding will be determined by visual estimation of the percentage (%) (to the nearest 5%) of parenchymal involvement in each zone, from 0 to 100. A total sum of all abnormalities in one zone of a lung cannot exceed 400%.

The score for each zone will be calculated by multiplying the percentage of the area by the mentioned above grading scale score (1-4). The zone scores for six zones of two lungs will be averaged to determine the total score for each patient. The overall HRCT score should be obtained by adding the averages for each index. The highest possible score is 400 points and the lowest score is 100 points using this calculation method.

The total score will be named as the “HRCT fibrosis score”. Semiquantitative assessment with HRCT fibrosis score calculation will be performed at initiation of treatment and 6 months later. For patients continuing therapy in real clinical practice after study completion additional assessment will be performed in a year of therapy.

Pirfenidone—F. Hoffmann-La Roche Ltd

Appendix 2

HRCT Protocol (cont.)

Table 1-3. Assessment of HRCT UIP signs in lungs.

Sign	Reticular abnormality	Honeycombing	Traction bronchiectases	Normal attenuation	Lung opacity
Upper zone RL ¹					
Middle zone RL					
Lower zone RL					
Upper zone LL ²					
Middle zone LL					
Lower zone LL					

¹ RL – right lung.

² LL – left lung.

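### The HRCT baseline is defined inconsistently and may predate the first dose by up to 2 months, so change before pirfenidone can be reported as on-treatment change

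*Protocol*

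**What the plan says.** **Which scan is used.** Protocol 4.5.6.1 states: "Baseline HRCT scans will be performed only in those patients who have no acceptable scans within 2 months before the start of treatment period". The same sentence adds the condition "and had no IPF exacerbations within this period". The Screening list in Protocol 4.5.13.2 foresees a baseline scan "for patients with HRCT scans performed more than 2 months before the treatment period or with scans not meeting the imaging acquisition criteria", with no mention of exacerbations. Footnote 9 of Appendix 1, repeated under the SAP's schedule of activities, reads: "HRCT should be performed at the Screening only for patients having no validated procedure within 2 months prior initiation of treatment". It does not mention exacerbations either.

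**When the score is recorded.** Protocol 6.4.3 and SAP 8.3 share one sentence: "Score will be recorded at the initial diagnosis and after six and 12 months in a similar manner for further comparison". The sentence after it, in both documents, speaks of baseline instead. Appendix 2 gives two further versions: "Semiquantitative assessment with HRCT fibrosis score calculation will be performed at initiation of treatment and 6 months later" and "HRCT is performed at initiation of the participation in the study and at the end of treatment".

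**How it is analysed.** SAP 8.3 summarises the change in fibrosis score and in lung opacity score from baseline to Week 26 and Week 52 with 95% CIs. It tests the change in fibrosis score by paired t-test at 5%. SAP section 7 defines a general baseline but excepts efficacy analysis. SAP 8.1 and 8.2 supply specific baselines for FVC, 6MWT, Borg and EQ-5D. SAP 8.3 supplies none for HRCT, and the footnotes of Tables 2.15 and 2.16 are silent.

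**The concern.** Protocol 1.1 describes IPF as progressive. Any time between the baseline scan and the first dose therefore adds change that pirfenidone could not have influenced, and that change is reported as change from baseline to Week 26. There is no control arm in which a shifted baseline would cancel out. The length of the gap also differs between patients, from almost nothing to about 2 months, so the mean change mixes intervals of different length.

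The gap is specific to HRCT. FVC, 6MWT and Borg use the average of Screening and Day 1, and FVC, 6MWT, Borg and EQ-5D each get a rerun restricted to visit windows. HRCT gets no analysis by scan timing.

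Exacerbations are a second problem. Appendix 2 says that an exacerbation adds opacity or consolidation, and that "In some cases honeycombing reduces partially or completely due to effusion in the cysts". Honeycombing carries the highest grade in the fibrosis score. If an exacerbation falls between the baseline scan and Day 1, an event from before treatment can enter both HRCT scores as on-treatment change. No passage says how such a scan is to be handled.

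At stake is the reading of the HRCT results, including the only hypothesis test in the plan.

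**Working it through.** **The plan's own figures.** The plan has no sample size, SD or rate of change for HRCT. Its sample-size figure concerns FVC and reproduces: 0.601 × 0.399 × (1.96/0.125)² = 58.96, rounded up to 60. It does not depend on the HRCT baseline.

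**Inputs.**
- Maximum age of an accepted baseline scan: 2 months before Day 1 (Protocol 4.5.6.1, 4.5.13.2, Appendix 1). 2 × 365.25/12/7 = 8.7 weeks.
- Screening: up to 4 weeks (Protocol 3.1).
- Follow-up scans: Week 26 ± 1, and Week 52 for rollover patients (Appendix 1).

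**Step 1. Share of the interval before the first dose** = gap / (gap + follow-up time).

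| Baseline scan | To Week 26 | To Week 52 |
|---|---|---|
| Day 1 | 0% | 0% |
| 4 weeks before (start of Screening) | 4/30 = 13% | 4/56 = 7% |
| 2 months before | 8.7/34.7 = 25% | 8.7/60.7 = 14% |

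With the Week 26 scan at Week 25 or Week 27, the 2-month share is 26% or 24%.

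**Step 2. Size of the overstatement.** At a constant rate of change (assumption), a patient with a 2-month-old scan shows 34.7/26 = 1.33 times the true 26-week change, which is one third too much. This is the upper limit under that assumption, because it needs every scan to be at the full 2 months. If change is slower on pirfenidone, the part of the measured change that came before the first dose is 8.7/(8.7 + 26k), where k is the on-treatment rate relative to the earlier rate. For k = 0.75, 0.5 and 0.25 (assumed) this gives 31%, 40% and 57%.

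**Step 3. Effect on the paired t-test.** Assume n = 60, a two-sided 5% test and no true on-treatment change. Let D be the change before treatment, in SDs of the paired difference per 26 weeks. The spurious standardised shift is D × gap/26, and the rejection rate follows from the noncentral t distribution with noncentrality equal to that shift times √60.

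| D (assumed) | Every scan 8.7 weeks old | Every scan 4 weeks old |
|---|---|---|
| 0.1 | 5.7% | 5.2% |
| 0.25 | 9.8% | 6.0% |
| 0.5 | 25% | 9.0% |
| 1.0 | 72% | 22% |

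The documents do not say where D lies, and not every scan will be at the limit. The table shows sensitivity, not an expected error rate.

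**Step 4. The exacerbation clause beside the other rules.** Take a patient with no acceptable scan within 2 months and an exacerbation in that period. Read literally, Protocol 4.5.6.1 gives this patient no baseline scan; 4.5.13.2 and footnote 9 (protocol and SAP) do give one. Now take a patient with an acceptable scan followed by an exacerbation. None of these passages says whether that scan remains the baseline.

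**The case against.** The strongest defence is that the plan does cap the gap. Four places, one of them in the SAP, limit an existing scan to 2 months before treatment, and Appendix 2 speaks of the start of treatment. Initial diagnosis looks like a loose phrase that its own next sentence corrects. SAP 7.3 and 8.3 also keep the eligibility scan and the scored scan on separate eCRF forms. This stands. A reader might infer that the HRCT baseline is not tied to the start of treatment at all, or that a diagnostic scan as old as the 24-month limit could serve. The documents do not support that: the 24-month limit is stated for eligibility, and a scan older than 2 months triggers a new baseline scan.

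A reader might also infer that patients with a recent exacerbation get no baseline scan. That is one reading of one clause. The clause could equally mean that a recent scan suffices only if no exacerbation occurred, and the other rules contain no such exception. Exclusion criterion 1 removes patients with significant worsening between Screening and Day 1 in the investigator's opinion, and Protocol 3.3.5 expects exacerbations to be infrequent. Few patients would be affected. A baseline taken soon after an exacerbation could also bias the other way, since raised opacity may later clear. So it does not follow that a rescan should be required.

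Finally, the added change points towards worsening and so does not flatter the drug, the endpoint is exploratory, and a single-arm test against zero cannot isolate a drug effect in any case. All true. But the 25% arises within the cap, not outside it, and the SAP still has neither a rule for choosing the baseline scan nor an analysis by scan age. Exclusion 1 covers at most 28 days of the 2 months.

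**Conclusion.** The concern holds as a problem of definition with a bounded effect. The HRCT baseline is loosely and inconsistently tied to the start of treatment, and SAP 8.3 does not settle which scan it is. Followed as written, the plan allows up to 25% of the baseline-to-Week-26 interval to fall before pirfenidone. At a constant rate of change this overstates the 26-week change by at most one third. The actual bias is probably smaller, because not every scan will be 2 months old, but it cannot be calculated without a rate of change or an SD for the score.

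The exacerbation clause in Protocol 4.5.6.1 is ambiguous and conflicts with 4.5.13.2 and footnote 9, and the handling of a scan that precedes an exacerbation is undefined.

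The pre-dose interval should be described as time before pirfenidone. A reader might call it untreated, but other IPF therapy may run until the 28-day washout, and corticosteroids up to 15 mg/day of prednisolone or equivalent are permitted throughout (Protocol 3.1, 4.4.1).

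The weight is moderate. HRCT is exploratory, although it carries the only planned test. The FVC primary endpoint and the sample size of 60 are not affected.

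**What to change.** 1. In Protocol 6.4.3 and SAP 8.3, replace the reference to initial diagnosis with baseline, defined as the last acceptable scan before the first dose within the 2-month limit already stated. Bring the two timing statements in Appendix 2 into line, and add the definition to the footnotes of Tables 2.15 and 2.16.
2. Reconcile the exacerbation clause in Protocol 4.5.6.1 with 4.5.13.2 and with footnote 9 in the protocol and SAP, and state how a baseline scan that precedes an exacerbation is treated in the analysis. Whether any further scan is done is a clinical decision and is not proposed here.
3. Summarise the days from baseline scan to Day 1. Add one sensitivity run of Tables 2.15 and 2.16, either limited to scans within 28 days before Day 1 (pre-dose share at most 13%) or with change scaled to 26 weeks, which assumes linear change. Leave out patients whose baseline scan is known to precede an exacerbation.

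The cost is wording plus one extra table run with fewer patients. Listing 22 already carries the scan date and study day, so the timing summary needs no new data. Exacerbations before the first dose can be identified only as far as the medical history records them, because Protocol 5.3.1 limits adverse event reporting in that period to serious events caused by protocol procedures.
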